5.1. Co-Primary Efficacy Endpoints

- Proportion of subjects with an IGA success (defined as an IGA of 0 [clear] or 1 [almost clear] and a ≥ 2 -point reduction from Baseline) at Week 16
- Proportion of subjects with EASI-75 ($\geq 75\%$ improvement in EASI from Baseline) at Week 16

5.2. Key Secondary Efficacy Endpoints

- Proportion of subjects with an improvement of PP NRS ≥ 4 at Week 16
- Proportion of subjects with PP NRS < 2 at Week 16

CCI

[figure not shown]

This document is confidential.

1.0

CD14152.SPR118161.SAP.V01

[figure not shown]
Approved 10-Nov-2022 00:00:00

CCI

This document is confidential.

CCI

[figure not shown]

1.0

CD14152.SPR118161.SAP.V01

Approved 10-Nov-2022 00:00:00

This document is confidential.

CCI

5.4. Pharmacokinetic Endpoints

- Nemolizumab (CD14152) serum concentrations

5.5. Safety Endpoints

- Incidence and severity of AEs, including AESIs, TEAEs, and SAEs
- Physical examination and Vital signs
- Clinical laboratory tests
- Electrocardiogram
- Peak expiratory flow
- Asthma Control Test (ACT)

5.6. Other Endpoints

5.6.1. Immunogenicity

- Anti-drug antibody (ADA) concentrations
- Incidence of positive ADA assays

This document is confidential.

6. Analysis Sets

For Initial Period and Maintenance Period, the following populations will be defined for analysis. Only subjects who are re-randomized after Initial Period will be included in the analysis population of Maintenance Period.

6.1. Intent-to-Treat Population

The intent-to-treat (ITT) population will consist of all randomized subjects. All primary and secondary efficacy endpoints will be analyzed based on the ITT population.

For Maintenance Period, the ITT population will include subjects who are re-randomized after Initial Period.

The ITT population will be the primary population for all efficacy analyses. All analyses on the ITT population will be analyzed under the treatment group 'as randomized'. If a subject is stratified incorrectly, 'stratum at the randomization' will be used rather than 'actual stratum' for analysis or summary of efficacy data.

6.2. Enrolled Subjects in Maintenance Period Population

The enrolled subjects in maintenance period population will comprise all subjects in ITT Population who are re-randomized or continue on Placebo after initial period.

6.3. Safety Population

The safety population will comprise all subjects in ITT population who receive at least 1 dose of study drug. All safety data will be summarized based on the safety population under the treatment group 'as treated'.

For Maintenance Period, only subjects in ITT population who received at least one drug in the Maintenance Period will be included in the population.

Subject who are treated on error during the course of the study will be assigned to actual treatment as described below.

Initial Period:

- Subjects who are randomized to Placebo but treated at least once with Nemolizumab in error will be assigned to 'Nemolizumab Q4W'.
- Subjects who are randomized to Nemolizumab but treated at least once with Placebo in error will still be assigned to 'Nemolizumab Q4W'. If they always received Placebo in error during the period, then they will be assigned to 'Placebo'.

Maintenance Period:

- Subjects who are re-randomized to Nemolizumab Q4W but treated at least once with Placebo in error will be assigned to 'Nemolizumab Q4W to Q4W'.
- In case of subjects who re-randomized to Nemolizumab Q8W, they are supposed to receive Nemolizumab and Placebo alternately. If they are treated with Nemolizumab instead of Placebo at least once in error, they will be assigned to 'Nemolizumab Q4W to Q4W'. However if they are treated

This document is confidential.

at least once with Placebo instead of Nemolizumab in error will be assigned to 'Nemolizumab Q4W to Q8W'.

- Subjects who are re-randomized to Placebo but treated with Nemolizumab at least once in error will be assigned to 'Nemolizumab Q4W to Q4W'.
- Subjects who are randomized to Placebo for Initial Period and continue the Maintenance Period will be assigned to 'Placebo' even if treated with Nemolizumab at least once in error.

Overall Period:

- If subjects exited the study after Initial Period (i.e., not re-randomized nor continued with Placebo for Maintenance Period), overall period treatment group will be the same with Initial period treatment group assigned (i.e., can be either 'Nemolizumab Q4W' or 'Placebo').
- In case subjects who re-randomized for Maintenance Period,
 - Subjects who are re-randomized to Nemolizumab Q4W will be assigned to 'Nemolizumab Q4W' even if they treated by Placebo in error during the study.
 - Subjects who are re-randomized to Nemolizumab Q8W will be assigned to 'Nemolizumab Q4W to Q8W' if the error occurred during Initial Period. When the error is occurred during Maintenance Period, overall period treatment group will be 'Nemolizumab Q4W to Q8W' if receive Placebo instead of Nemolizumab or 'Nemolizumab Q4W' if receive Nemolizumab instead of Placebo during Maintenance Period.
 - Subjects who are re-randomized to Placebo will be assigned to 'Nemolizumab Q4W to Placebo' if the error is occurred in Initial Period. However if the error is occurred during Maintenance Period, the overall treatment group will be 'Nemolizumab Q4W'.
- Subjects who are randomized to Placebo for Initial Period and continue the Maintenance Period will be assigned to 'Placebo'.

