10.1.1.2 Safety Population

The safety population will comprise all subjects in ITT population who receive at least 1 dose of study drug. All safety data will be summarized based on the safety population under the treatment group ‘as treated’.

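### SAP 6.3 promises assignment to actual treatment but leaves placebo-continuation subjects in Placebo after an erroneous nemolizumab dose, unlike its other mis-dosing rules

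*SAP*

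**What the plan says.** Protocol 10.1.1.2 sets the principle: "All safety data will be summarized based on the safety population under the treatment group" as treated. SAP 6.3 repeats it and adds that subjects treated in error "will be assigned to actual treatment as described below". The rules for nemolizumab given to a subject assigned placebo then read as follows.

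- **Initial Period.** "Subjects who are randomized to Placebo but treated at least once with Nemolizumab in error will be assigned to" the Nemolizumab Q4W group.
- **Maintenance Period, re-randomized to placebo (group 1C).** One erroneous nemolizumab dose moves the subject to 'Nemolizumab Q4W to Q4W'.
- **Maintenance Period, placebo from the start.** The continuing subject is placed in Placebo "even if treated with Nemolizumab at least once in error".
- **Overall Period, subject exits after the Initial Period.** The Initial Period group is kept, so a mis-dosed placebo subject stays in Nemolizumab Q4W.
- **Overall Period, subject continues.** "Subjects who are randomized to Placebo for Initial Period and continue the Maintenance Period will be assigned to" Placebo. No provision is made for a dosing error in either period.

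SAP 15, which lists changes from the protocol's planned analysis, mentions only the definition of concomitant medication. No reason is given for treating continuing placebo subjects differently.

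**The concern.** The exception is assignment as randomized inside a section that promises assignment as treated. Adverse events that follow an erroneous active dose would be tabulated under the comparator. For any event the drug causes, that raises the placebo rate and narrows the apparent difference.

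Exposure after one dose is not brief. Protocol 8.1 equates 12 weeks with about 5 half-lives, and the Maintenance Period lasts 32 weeks. There is also a signal to protect: Protocol 6.3 reports phase 2b asthma flares in 1.8% of the placebo arm and 12.3% of the 30 mg arm, among subjects with pre-existing asthma, and asthma is an adverse event of special interest here.

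The Overall rule adds a second problem. Continuing on placebo requires a Week 16 response. Two placebo subjects with the same Initial Period dosing error can therefore land in different Overall columns according to a post-randomization outcome.

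**Working it through.** **Step 1. The rules side by side.** In each row the subject was assigned placebo and received nemolizumab at least once in error.

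| Subject | When the error occurs | Table | Group under SAP 6.3 |
|---|---|---|---|
| Initial placebo | Initial | Initial | Nemolizumab Q4W |
| Initial placebo, exits | Initial | Overall | Nemolizumab Q4W |
| Initial placebo, continues | Initial | Overall | Placebo |
| Initial placebo, continues | Maintenance | Maintenance | Placebo |
| Initial placebo, continues | Maintenance | Overall | Placebo |
| Re-randomized to placebo (1C) | Maintenance | Maintenance | Nemolizumab Q4W to Q4W |
| Re-randomized to placebo (1C) | Maintenance | Overall | Nemolizumab Q4W |

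Only the three rows for continuing placebo subjects depart from actual treatment. The second and third rows differ only in whether the subject continued.

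**Step 2. The size of the group.** Protocol 8.1 gives 750 subjects randomized 2:1, 15% dropout in the initial period, and responder rates of 45% (nemolizumab) and 12% (placebo). Expected number = N × allocation × (1 − dropout) × responder rate.

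- Nemolizumab: 750 × 2/3 × 0.85 × 0.45 = 191.25 (stated: 190).
- Placebo continuation: 750 × 1/3 × 0.85 × 0.12 = 25.5 (stated: 26).
- Total: 216.75 (stated: 216).

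The protocol's figures reproduce.

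**Step 3. Effect per affected subject.**

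- Maintenance, continuation group: 1/26 = 3.8 percentage points.
- Overall Placebo column, taking the planned 750/3 = 250: 1/250 = 0.4 points.
- Example with one genuine placebo case and one case after a mis-dose: 2/26 = 7.7% under the SAP rule. It is 1/26 = 3.8% if the later event is counted elsewhere but the subject stays in the denominator for the pre-error time, or 1/25 = 4.0% if the subject is removed altogether.

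**Step 4. How often it might arise.** The documents give no dosing-error rate. *Assumption:* an error probability e per injection of 0.1% to 1%, independent across the 8 Maintenance injections (Weeks 16 to 44). Expected mis-dosed subjects = 26 × [1 − (1 − e)^8]; probability of at least one = 1 − (1 − e)^(26 × 8).

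| e | Expected subjects | Probability of at least one |
|---|---|---|
| 0.1% | 0.2 | 0.19 |
| 0.5% | 1.0 | 0.65 |
| 1% | 2.0 | 0.88 |

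Over that range the rule would touch between none and about two subjects.

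**The case against.** Several points count against making more of this.

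- **The exception may follow the column labels.** The Maintenance nemolizumab labels ('Q4W to Q4W', 'Q4W to Q8W') presuppose nemolizumab in the Initial Period, and none of the four Overall groups in SAP 13.1 describes placebo followed by nemolizumab. A continuing placebo subject with one stray dose fits the SAP 13.1 description of Placebo best. This is a plausible motive, but the SAP does not state it, and a lack of suitable columns does not make the assignment as treated.
- **Moving the whole subject to nemolizumab would misclassify in the other direction.** It would carry placebo person-time and pre-error events into the drug column. This objection stands and shapes the fix below.
- **The Overall bullet is silent, not explicit.** Unlike the Maintenance bullet, it has no clause covering erroneous dosing, so the clash with the Initial Period assignment comes from its plain wording. At the least it needs clarifying.
- **Continuing subjects may be outside the population.** SAP 6.1 limits the Maintenance ITT population to re-randomized subjects, and the Maintenance safety population is drawn from ITT. But the disputed bullet assigns these subjects a group, SAP 6.2 and 6.4 include them, and the Overall rule names them.
- **Any case would be traceable.** Improper administration is a major-deviation category (Protocol 10.3), and drug administration and treatment-emergent events are listed by subject. The information is not lost; only the summary tables are affected.

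A reader might also infer that the trial's main drug-placebo safety contrast is biased. The documents do not support that. Initial Period tables already move mis-dosed placebo subjects to nemolizumab, and so do the Maintenance rules for group 1C, the randomized placebo comparator. Continuing placebo subjects are a non-randomized group of placebo responders. Nor does the Maintenance rule sort subjects by response, since everyone in that period responded at Week 16. That complaint applies only to the Overall handling of Initial Period errors.

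**Conclusion.** SAP 6.3 is internally inconsistent. Its stated principle and its parallel rules go by actual treatment; its rule for continuing placebo subjects does not, and its Overall rule can contradict its own Initial Period assignment. If an error occurs, each affected case shifts the projected continuation column by 3.8 points and an Overall Placebo column of about 250 by about 0.4 points. If none occurs, no result changes.

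These sizes rest on the protocol's projection of 26 continuing subjects, on the planned placebo allocation of 250, and on the mis-dosed subject actually having the event in question. The bias is toward no difference only for events that the drug causes. It would be wrong to conclude that drug-exposed events are already being counted under placebo: the documents report no such error. This is a minor point, but a stated rule that is easily corrected.

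**What to change.** Remove the exception in SAP 6.3 and settle the wording before unblinding.

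- In Maintenance and Overall safety tables, take a placebo-continuation subject who received any nemolizumab out of the Placebo column from the first erroneous dose onward. Count later events and exposure time in a separate category such as 'Placebo with nemolizumab exposure'. Earlier events and time stay under Placebo.
- Carry an Initial Period reassignment into the Overall Period whether or not the subject continues.
- Add the new category to the Overall groups in SAP 13.1, and state how the denominator is split for percentages and for exposure-adjusted rates.

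The cost is SAP text, some programming, and one small extra column or split denominator that may well be empty. No new data are needed. If the sponsor prefers to keep the exception, the SAP should justify it, record it in section 15 as a departure from the protocol's as-treated rule, and footnote every affected subject.

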6.4. Enrolled Safety Subjects in Maintenance Period Population

The enrolled safety subjects in maintenance period population will comprise only subjects in enrolled subjects in maintenance period population who received at least one drug in the maintenance period.

6.5. PK Analysis Population

The PK analysis population will include all subjects in the safety population who provide at least 1 post-Baseline evaluable drug concentration value and not include any biologically implausible value.

For Maintenance Period, only subjects in the safety population who provide at least 1 post-Week 16 evaluable drug concentration and not include any biologically implausible value in the Maintenance Period will be included in the population.

All PK and ADA endpoints will be analyzed using the PK analysis population under the treatment group 'as treated'.

6.6. Enrolled PK Subjects in Maintenance Period Population

The enrolled PK subjects in maintenance period population will comprise only subjects in enrolled Safety subject in maintenance period population who provide at least 1 post-week 16 evaluable drug concentration value and not include any biologically implausible value.

This document is confidential.

6.7. Per-Protocol Population

The per-protocol (PP) population will comprise all subjects in the ITT population who have no major protocol deviations that would have a significant effect on the efficacy of the study treatment. Only primary and key secondary endpoints will be analyzed using the per-protocol population under the treatment group 'as randomized'.

6.8. PD Analysis Population

The PD analysis population(s) will be described in a separate pharmacodynamic plan by designated CRO.

6.9. Protocol Deviations

Protocol deviations will be recorded by the Clinical Research Associate (CRA) in the Clinical Trial Management System (CTMS). All protocol deviations will be categorized by deviation type which the deviation is associated with, and will be assessed individually on a regular basis on whether they are important (major) or non-important (minor). Details can be found in the Protocol Deviation and Non-compliance Management Plan.

Major protocol deviations would lead to an exclusion of the subject from the per-protocol population. A case by case decision regarding exclusions of subjects from the per-protocol population will be made in a blind data review meeting (BDRM) which will take place prior to unblinding the study.

Individual deviations (major and minor) will be presented in a data listing on the ITT population. A summary table for number and percentage of subjects with major protocol deviation will be summarized by type of deviation and treatment group for the Initial Period and the Maintenance Period for the ITT population.

Protocol deviations incurred as a direct result of the COVID-19 pandemic should be specifically recorded and presented as a COVID-19 deviation. The number and percentage of subjects with major COVID-19 deviation will be provided by type of deviation and treatment group for the Initial Period and the Maintenance Period for the ITT population.

Major protocol deviations will also be summarized by site for the ITT population.

This document is confidential.

7. Estimands

The co-primary and key secondary efficacy endpoints will be evaluated in the moderate-to-severe atopic dermatitis represented by the study inclusion/exclusion criteria and assigned to treatment during initial period. The estimand is defined to address the scientific question relevant to subjects who are able to complete treatment with a response assessment without further medication being required, other than the allowed background and rescue medication.

An intercurrent event is an event which occurs after start of treatment and thus complicates the description and interpretation of treatment effects. Table 7-1 below lists potential intercurrent events and the strategy to deal with them for the estimand. Estimands for the co-primary and key secondary endpoints are listed in Tables 7-2 and 7-3.

Table 7-1 List of Intercurrent Events

Intercurrent Event	Strategy to Deal With Intercurrent Event Within Analysis	Assessment of Subject

	Intercurrent events: use of rescue therapies prior to Week 16 is considered as non-responder; the observed response at Week 16 after treatment discontinuation will be used in the analysis.
	Summary measure: treatment difference of nemolizumab and placebo in response rate
Proportion of subjects with PP NRS < 2 at Week 16	Population: ITT population (Full population; Baseline PP NRS ≥ 7)
	Endpoint: a binary response indicates if subjects with PP NRS < 2 at Week 16
	Intercurrent events: use of rescue therapies prior to Week 16 is considered as non-responder; the observed response at Week 16 after treatment discontinuation will be used in the analysis.
	Summary measure: treatment difference of nemolizumab and placebo in response rate
	Population: ITT population (Full population; Baseline PP NRS ≥ 7)

This document is confidential.

1.0

CD14152.SPR118161.SAP.V01

Approved 10-Nov-2022 00:00:00

Endpoints	Estimands
Proportion of subjects with an improvement of SD NRS ≥ 4 at Week 16	Endpoint: a binary response indicates if subjects with an improvement of SD NRS ≥ 4 at Week 16
	Intercurrent events: use of rescue therapies prior to Week 16 is considered as non-responder; the observed response at Week 16 after treatment discontinuation will be used in the analysis.
	Summary measure: treatment difference of nemolizumab and placebo in response rate
Proportion of subjects with an improvement of PP NRS ≥ 4 at Week 4	Population: ITT population (Full population; Baseline PP NRS ≥ 7)
	Endpoint: a binary response indicates if subjects with an improvement of PP NRS ≥ 4 at Week 4
	Intercurrent events: use of rescue therapies prior to Week 4 is considered as non-responder; the observed response at Week 4 after treatment discontinuation will be used in the analysis.
Proportion of subjects with PP NRS < 2 at Week 4	Population: ITT population (Full population; Baseline PP NRS ≥ 7)
	Endpoint: a binary response indicates if subjects with PP NRS < 2 at Week 4
	Intercurrent events: use of rescue therapies prior to Week 4 is considered as non-responder; the observed response at Week 4 after treatment discontinuation will be used in the analysis.
Proportion of subjects with an improvement of PP NRS ≥ 4 at Week 2	Population: ITT population (Full population; Baseline PP NRS ≥ 7)
	Endpoint: a binary response indicates if subjects with an improvement of PP NRS ≥ 4 at Week 2
	Intercurrent events: use of rescue therapies prior to Week 2 is considered as non-responder; the observed response at Week 2 after treatment discontinuation will be used in the analysis.
Proportion of subjects with an improvement of PP NRS ≥ 4 at Week 1	Population: ITT population (Full population; Baseline PP NRS ≥ 7)
	Endpoint: a binary response indicates if subjects with an improvement of PP NRS ≥ 4 at Week 1
	Intercurrent events: use of rescue therapies prior to Week 1 is considered as non-responder; the observed response at Week 1 after treatment discontinuation will be used in the analysis.

This document is confidential.

Endpoints	Estimands
	Summary measure: treatment difference of nemolizumab and placebo in response rate
Proportion of subjects with EASI-75 and improvement of PP NRS ≥ 4 at Week 16	Population: ITT population (Full population; Baseline PP NRS ≥ 7)
	Endpoint: a binary response indicates if subjects with EASI-75 and improvement of PP NRS ≥ 4 at Week 16
	Intercurrent events: use of rescue therapies prior to Week 16 is considered as non-responder; the observed response at Week 16 after treatment discontinuation will be used in the analysis.
	Summary measure: treatment difference of nemolizumab and placebo in response rate
Proportion of subjects with IGA success and improvement of PP NRS ≥ 4 at Week 16	Population: ITT population (Full population; Baseline PP NRS ≥ 7)
	Endpoint: a binary response indicates if subjects with IGA success and improvement of PP NRS ≥ 4 at Week 16
	Intercurrent events: use of rescue therapies prior to Week 16 is considered as non-responder; the observed response at Week 16 after treatment discontinuation will be used in the analysis.
	Summary measure: treatment difference of nemolizumab and placebo in response rate

This document is confidential.

8. General Aspects for Statistical Analysis

8.1. General Methods

All data will be listed, and summary tables will be provided. Summaries will be presented for each treatment and visit (if applicable).

Unless otherwise stated, continuous variables will be summarized using the number of observations (n), mean, standard deviation (SD), median, Q1, Q3, minimum, and maximum by treatment group and visit (if applicable). Categorical variables will be summarized using frequency and percentages of subjects for each category by treatment group and visit (if applicable).

Unless otherwise stated, all statistical tests will be 2-sided and conducted at the 5% level; all presented confidence intervals (CIs) will be 2-sided 95% CIs.

8.2. Key Definitions

Screening Period is a Period of approximately 2-4 weeks before Day 1/Baseline during which subject eligibility is evaluated and standardized background topical therapy is introduced over a run-in Period of at least 2 weeks before Day 1/Baseline.

The Initial Period is defined as Day 1/Baseline to Week 16 (before the Week 16 dose, with last dose at Week 12). If early discontinued during treatment period, it is defined as the period until 4 weeks after last dosing date or early termination date whichever is earlier.

The Maintenance Period is defined as Week 16 (Maintenance Baseline) to Week 48. If early discontinued during treatment period, it is defined as the period until 4 weeks after last dosing date or early termination date whichever is earlier.

Follow-up Period is defined as the post end of treatment period (i.e., 1 day after end of treatment period) to Follow-up visit in respective treatment period.

The Baseline value of the Initial Period will be taken as latest valid value prior to first injection of study drug. For subjects randomized but not treated, the Baseline value will be the latest value prior to the randomization. Week 16 measurements will serve as Baseline measurements for the Maintenance Period (i.e., Maintenance Baseline). If Week 16 measurements are missing for re-randomized subjects, the last valid non-missing measurement in the Initial Period (i.e., before the dosing for Maintenance Period at Week 16 visit) will be taken as the Baseline measurement for the Maintenance Period.

For diary data (e.g., Peak Pruritus (PP) NRS, Sleep disturbance (SD) NRS), the Baseline values will be the weekly prorated average of non-missing subject diary scores reported during the 7 days. A minimum of 4 daily scores out of the 7 days is required to calculate the weekly prorated average score. Refer the details for the analysis visit window for diary data in Section 8.4.

The date of first treatment is defined as the date of first injection of study drug. The date of first treatment is the Baseline date.

The date of last treatment is defined as the date of last injection of study drug.

Study day is defined as the number of days from the date of first treatment and will be calculated as follows:

This document is confidential.

- If the event date \geq date of first treatment, study day = event date – date of first treatment + 1. Study Day 1 is therefore defined as the day of first treatment.
- If the event date $<$ date of first treatment, study day = event date – date of first treatment.

A subject's date of last participation in the trial is the last date of contact.

